Appendix H Immune-Related Response Criteria: irRECIST

Tumor response will be assessed using the Immune-Related response Criteria as described by Nishino et al, (14) and Bohnsack et al, (13).

1 Baseline

1.1 Measurable Lesion Definitions and Target Lesion Selection

- All measurable lesions up to a maximum of 2 lesions per organ and 5 lesions in total, representative of all involved organs, will be identified as target lesions and recorded and measured at baseline
- Measurable lesions must be accurately measured in at least one dimension with a minimum size of:
 - 10 mm in the longest diameter by CT or MRI scan (or no less than double the slice thickness) for non- nodal lesions and ≥ 15 mm in short axis for nodal lesions.
 - 10 mm caliber measurement by clinical exam (lesions which cannot be accurately measured with calipers should be recorded as non-measurable).
 - 20 mm by chest X-ray
- A sum of the longest diameter (short axis for lymph nodes) of all target lesions will be calculated and reported as the baseline sum diameters. This will be used as reference to further characterize the objective tumor response of the measurable dimension of the disease.

1.2 Non-measurable Lesion Definitions

- Non-target lesions will include:
 - Measurable lesions not selected as target lesions
 - All sites of non-measurable disease, such as neoplastic masses that are too small to measure because their longest uninterrupted diameter is < 10 mm (or $<$ two times the axial slice thickness), i.e., the longest perpendicular diameter is ≥ 10 and < 15 mm.
 - Other types of lesions that are confidently felt to represent neoplastic tissue but are difficult to measure in a reproducible manner. These include bone metastases, leptomeningeal metastases, malignant ascites, pleural or pericardial effusions, ascites, inflammatory breast disease, lymphangitis cutis/pulmonis, cystic lesions, ill-defined abdominal masses, skin lesions, etc.
- All lesions or sites of disease not recorded as target lesions (e.g., small lesions and non-measurable lesions) should be identified as non-target lesions and indicated as present in the source documents at baseline. There is no limit to the number of non-target lesions that

can be recorded at baseline. The general location will also be documented on the images, drawing a regularly-shaped Region of Interest.

- Measurements of the non-target lesions will not be performed, but the presence or absence of each should be noted throughout follow-up and evaluation.

1.3 Target and Non-Target Lymph Node Lesion Definitions

- To be considered pathologically enlarged and measurable, a lymph node must be ≥ 15 mm in short axis when assessed by CT scan (CT scan slice thickness recommended to be no greater than 5 mm). At baseline and in follow-up, only the short axis will be measured and followed.

1.4 Non-Target Lesion Selection

- All lesions or sites of disease not recorded as target lesions should be recorded as non-target lesions at baseline. There is no limit to the number on non-target lesions that can be recorded at baseline.

1.5 Bone Lesions

- Bone scan, PET scan or plain films are not considered adequate imaging techniques to measure bone lesions. However, these techniques can be used to confirm the presence or disappearance of bone lesions.
- Regardless of the imaging modality blastic bone lesions will not be selected as target lesions. Lytic or mixed lytic-blastic lesions with a measurable soft tissue component ≥ 10 mm can be selected as target lesions.

1.6 Brain Lesions

- Brain Lesions detected on brain scans can be considered as both target or non-target lesions.

1.7 Cystic and Necrotic Lesions as Target Lesions

- Lesions that meet the criteria for radiographically defined simple cysts should not be considered as malignant lesions (neither measurable nor non-measurable) since they are, by definition, simple cysts.
- Lesions that are partially cystic or necrotic can be selected as target lesions.
- The longest diameter of such a lesion will be added to the ***Total Measured Tumor Burden*** (TMTB) of all target lesions at baseline.

If other lesions with a non-liquid/non-necrotic component are present, those should be preferred.

1.8 Lesions with Prior Local Treatment

- During target lesion selection the radiologist will consider information on the anatomical sites of previous intervention (e.g. previous irradiation, RF-ablation, TACE, surgery, etc.).

Roswell Park Protocol No.: I 35316

- Lesions undergoing prior intervention will not be selected as target lesions unless there has been a demonstration of progress in the lesion.

1.9 No Disease at Baseline

- If a patient has no measurable and no non-measurable disease at baseline the radiologist will assign '**No Disease**' (irND) as the overall tumor assessment for any available follow-up time-points unless new measurable lesions are identified and contribute to the TMTB.

2 Follow-Up

2.1 Recording of Target and New Measurable Lesion Measurements

- The longest diameters of non-nodal target and new non-nodal measurable lesions, and short axes of nodal target and new nodal measurable lesions will be recorded. Together they determine the **Total Measured Tumor Burden (TMTB)** at follow-up.

2.2 Definition of New Measurable Lesions

- In order to be selected as new measurable lesions (≤ 2 lesions per organ, ≤ 5 lesions total, per time-point), new lesions must meet criteria as defined for baseline target lesion selection and meet the same minimum size requirements of 10 mm in long diameter and minimum 15 mm in short axis for new measurable lymph nodes. New measurable lesions shall be prioritized according to size, and the largest lesions shall be selected as new measured lesions.

2.3 Non-Target Lesion Assessment

- The RECIST 1.1 definitions (15) for the assessment of non-target lesions apply (i.e., measurements of the non-target lesions will not be performed, but the presence or absence of each should be noted throughout follow-up and evaluation).
- The response of non-target lesions primarily contributes to the overall response assessments of irCR and irNon-CR/Non-PD (irNN).
- Non-target lesions do not affect irPR and irSD assessments.
- Only a massive and unequivocal worsening of non-target lesions alone, even without progress in the TMTB is indicative of irPD.

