8.0 Study Endpoints

- The primary endpoint is the Overall Response Rate (ORR), defined as partial or complete response (per irRECIST) within 6 months of initiating combination therapy.
- The secondary endpoint is time to tumor progression (TTP), measured from the date of

study enrollment to the first observation of progressive disease.

- Exploratory endpoints: Pre-treatment levels of immunosuppressive cells and the functional activity of effector T cells will be compared to post-treatment blood and tumor samples and will be correlated with overall survival.

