16.0 Measurement of Effect

16.1 Solid Tumors

Tumor response will be assessed at Week 6 (\pm 1 week) and Week 12 (\pm 1 week) of combination therapy, and every subsequent 9 weeks (\pm 1 week) thereafter by immune-related response criteria (irRECIST) (13, 14). Conventional RECIST 1.1 (15) will also be documented during the trial, however RECIST 1.1 will not be used to determine disease progression, as it has been shown in prior clinical trials using pembrolizumab in large number of patients, that conventional RECIST might underestimate the benefit of pembrolizumab in approximately 15% of patients; thus using irRECIST could permit treatment beyond initial progression per RECIST v1.1 and prevent premature cessation of treatment.(14, 16, 17)

The irRECIST will be used for tumor response assessment at time of continuing review and will be used for IRB reporting and formal analysis.

Refer to Appendix H for a summary of tumor response assessment using irRECIST criteria.

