2.4 New Non-Measurable Lesions Definition and Assessment

- All new lesions not selected as new measurable lesions are considered new non-measurable lesions and are followed qualitatively.
- Only a massive and unequivocal progression of new non-measurable lesions leads to an overall assessment of irPD for the time-point.
- Persisting new non- measurable lesions prevent irCR.

2.5 irRECIST Overall Tumor Assessments

Roswell Park Protocol No.: I 35316

The irRECIST overall tumor assessment is based on the **TMTB** (total measured tumor burden) of measured target and new lesions, non-target lesion assessment and new non-measurable lesions.

- **irCR:** Complete disappearance of all measurable and non-measurable lesions. Lymph nodes must decrease to < 10 mm in short axis.
- **irPR:** Decrease of $\geq 30\%$ in TMTB relative to baseline, non-target lesions are irNN, and no unequivocal progression of new non-measurable lesions.
- **irSD:** Failure to meet criteria for irCR or irPR in the absence of irPD.
- **irNN:** No target disease was identified at baseline and at follow-up the patient fails to meet criteria for irCR or irPD.
- **irPD:** Minimum 20% increase and minimum 5 mm absolute increase in TMTB compared to nadir, or irPD for non-target or new non-measurable lesions. Confirmation of progression is recommended minimum 6 weeks after the first irPD assessment.
- **irNE:** Used in exceptional cases where insufficient data exists.
- **irND:** In adjuvant setting when no disease is detected.

New Lesions: the presence of new lesion(s) does not define progression. The measurements of the new lesion(s) are included in the sum of the measurements (the sum of the measurements = the sum of the longest diameters of all target lesions and new lesions, if any).

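### Appendix H gives two rules for irPR: read literally, section 2.5 turns some true partial responders into non-responders

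*Combined protocol and SAP*

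**What the plan says.** Section 8.0 sets the primary endpoint as overall response rate, "defined as partial or complete response (per irRECIST) within 6 months of initiating combination therapy". Section 16.1 points to the working criteria: "Refer to Appendix H for a summary of tumor response assessment using irRECIST criteria".

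Appendix H deals with non-target lesions in two places.

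- **Section 2.3:** "Non-target lesions do not affect irPR and irSD assessments". The next bullet sets the threshold for progression: "Only a massive and unequivocal worsening of non-target lesions alone, even without progress in the TMTB is indicative of irPD".
- **Section 2.5:** irPR needs a TMTB decrease of at least 30% and also that "non-target lesions are irNN, and no unequivocal progression of new non-measurable lesions". Overall irPD is triggered by growth in TMTB "or irPD for non-target or new non-measurable lesions".

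The abbreviation irNN has two meanings. Section 2.3 uses it as short for irNon-CR/Non-PD, a status to which non-target lesions contribute. The list in section 2.5 defines it as a category for the whole patient: "No target disease was identified at baseline and at follow-up the patient fails to meet criteria for irCR or irPD". Section 3.1 requires measurable disease at entry.

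Under section 19.1, the treatment is deemed effective if at least 4 of 27 evaluable patients respond.

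**The concern.** One sentence says that non-target status plays no part in irPR; the other makes it a condition of irPR. No text says which governs. They disagree for a patient who is doing well: target lesions down by at least 30% but still present, and non-target lesions gone. Those lesions are no longer Non-CR/Non-PD, so the irPR condition in 2.5 fails. irCR also fails because target disease remains. The patient then falls to irSD and counts as a non-responder. Better clearance of non-target disease earns a worse grade. A patient who had no non-target lesions at baseline meets the same difficulty, since there is nothing that could be irNN.

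irPR is one of the two ways to count as a responder, and the decision turns on a small count: 4 of 27 (14.8%) is a success and 3 of 27 (11.1%) is not. If a rule were chosen only after the scans had been read, the primary result could be challenged.

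**Working it through.** **Step 1. Reproduce the design.** Inputs from section 19.1: n = 27, success if X ≥ 4, null rate 0.05, alternative 0.20, stated power 80%, nominal one-sided error 5%.

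P(X ≥ 4 | 27, p) = 1 − Σ C(27,k) p^k (1−p)^(27−k), for k = 0 to 3.

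- At p = 0.20: 1 − (0.00242 + 0.01632 + 0.05304 + 0.11050) = 0.8177.
- At p = 0.05: 0.0437.

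The stated design reproduces, and the sample size is not in question.

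**Step 2. Set the two rules side by side.** Take a patient with a TMTB decrease of at least 30%, target disease still present, and no progression of new non-measurable lesions. Read irNN as Non-CR/Non-PD.

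| Non-target lesions | Section 2.3 | Section 2.5, literal |
|---|---|---|
| Persist, short of irPD | irPR | irPR |
| All disappeared | irPR | irSD |
| None at baseline | irPR | Condition cannot be met, so irSD |
| irPD | irPD | irPD |

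The rules differ in the second and third rows only. In both, 2.5 gives the lower grade.

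**Step 3. Size the effect.** The documents give no frequency for those two rows. Let m be the share of true responders who are denied irPR (an assumption). The observed response rate is then 0.20 × (1 − m), and power is P(X ≥ 4 | 27, 0.20(1 − m)). The expected number of responders lost is 27 × 0.20 × m = 5.4m.

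| Assumed m | Observed rate | Expected responders lost | Power |
|---|---|---|---|
| 0 | 0.20 | 0 | 81.8% |
| 5% | 0.19 | 0.27 | 78.2% |
| 10% | 0.18 | 0.54 | 74.2% |
| 20% | 0.16 | 1.08 | 64.7% |

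**Step 4. Type I error.** Losing responders lowers the observed rate under the null as well. P(X ≥ 4) rises with p, so the error cannot exceed 0.0437 by this route.

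**The case against.** The strongest reply is that a competent radiologist would not be misled. In section 2.5 the subject of the irPR condition is the lesions, and section 2.3 spells out irNN as Non-CR/Non-PD, so the lesion-level meaning is the natural one. On that reading the usual pattern, shrinking targets with persisting non-target lesions, is irPR under both sections. This stands. It disposes of the inference that no enrolled patient could ever be irPR because all must have measurable disease; that requires applying a patient-level label to lesions. It does not settle the cases of cleared or absent non-target lesions.

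A second reply is that Appendix H is only a summary, that it cites two publications for the criteria, and that it refers to RECIST 1.1 for non-target lesions. Those sources may resolve the matter, but they cannot be checked here, and a site grading from the protocol has two rules in front of it.

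Three stronger readings are tempting, and the documents do not support them:

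- **Inflated type I error.** A reader might infer that one patient graded upward lifts the false-positive rate to 13.9%, P(X ≥ 3 | 26, 0.05). That needs a mechanism for false irPR. The obvious one, overlooked non-target progression, is already irPD in both sections.
- **Power of 65% as the expected effect.** P(X ≥ 5 | 27, 0.20) = 0.652 assumes one true responder is lost in every trial, about one in 5.4. It is a severe case, not an estimate.
- **Divergence between sites.** Section 4.0 expects one centre to enroll 38 of 41 participants, so differences between sites could touch about three.

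**Conclusion.** The inconsistency is in the current text and affects a component of the primary endpoint. It is narrow: it concerns patients with target response, residual target disease, and non-target lesions that have cleared or were never present. The error runs one way, towards missed responders. If 5% to 20% of true responders were affected, power at a response rate of 0.20 would be 78.2% to 64.7% instead of 81.8%; even the 5% case falls below the stated 80%. These figures rest on assumed shares and on readers applying section 2.5 literally. If readers follow 2.3, nothing is lost. The sample size and cut-off are sound as they stand. The point is worth correcting because it lies in the primary endpoint and costs almost nothing to remove.

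**What to change.** Make three edits in Appendix H.

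1. In section 2.5, restate irPR along these lines: *TMTB down by at least 30% from baseline, with no irPD in non-target or new non-measurable lesions; non-target lesions may be absent, resolved or persistent.* This removes the irNN condition. It also ties new non-measurable lesions to irPD, as section 2.4 does; if the present condition on their unequivocal progression is meant as a lower bar, keep it.
2. In section 2.3, put *Short of irPD* at the head of the sentence "Non-target lesions do not affect irPR and irSD assessments", so that it agrees with the bullet after it and with 2.5.
3. Use separate terms for the Non-CR/Non-PD status of non-target lesions and for the patient-level category of no target disease at baseline.

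The cost is a few lines of text. The sample size, the cut-off and the irPD definition do not change. Any responses already graded with cleared or absent non-target lesions should be checked against the single rule.

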2.4 New Non-Measurable Lesions Definition and Assessment

- All new lesions not selected as new measurable lesions are considered new non-measurable lesions and are followed qualitatively.
- Only a massive and unequivocal progression of new non-measurable lesions leads to an overall assessment of irPD for the time-point.
- Persisting new non- measurable lesions prevent irCR.

2.5 irRECIST Overall Tumor Assessments

Roswell Park Protocol No.: I 35316

The irRECIST overall tumor assessment is based on the **TMTB** (total measured tumor burden) of measured target and new lesions, non-target lesion assessment and new non-measurable lesions.

- **irCR:** Complete disappearance of all measurable and non-measurable lesions. Lymph nodes must decrease to < 10 mm in short axis.
- **irPR:** Decrease of $\geq 30\%$ in TMTB relative to baseline, non-target lesions are irNN, and no unequivocal progression of new non-measurable lesions.
- **irSD:** Failure to meet criteria for irCR or irPR in the absence of irPD.
- **irNN:** No target disease was identified at baseline and at follow-up the patient fails to meet criteria for irCR or irPD.
- **irPD:** Minimum 20% increase and minimum 5 mm absolute increase in TMTB compared to nadir, or irPD for non-target or new non-measurable lesions. Confirmation of progression is recommended minimum 6 weeks after the first irPD assessment.
- **irNE:** Used in exceptional cases where insufficient data exists.
- **irND:** In adjuvant setting when no disease is detected.

New Lesions: the presence of new lesion(s) does not define progression. The measurements of the new lesion(s) are included in the sum of the measurements (the sum of the measurements = the sum of the longest diameters of all target lesions and new lesions, if any).

2.6 Confirmation Measurement

A confirmatory assessment is required no less than 6 weeks after an irPR or irCR is deemed by irRECIST (14)

3 Guidelines for Evaluation of Measurable Disease

All measurements should be taken and recorded in metric notation. All baseline evaluations should be performed as closely as possible to the beginning of treatment and never more than 4 weeks before the beginning of the treatment.

The same method of assessment and the same technique should be used to characterize each identified and reported lesion at baseline and during follow-up. Imaging-based evaluation is preferred to evaluation by clinical examination unless the lesion(s) being followed cannot be imaged but are assessable by clinical exam. The preferred imaging modality for this clinical trial is conventional CT scan using IV contrast.

- **Clinical Lesions:** Clinical lesions will only be considered measurable when they are superficial (e.g., skin nodules and palpable lymph nodes) and ≥ 10 mm diameter as assessed using calipers (e.g., skin nodules). In the case of skin lesions, documentation by color photography, including a ruler to estimate the size of the lesion, is recommended.
- **Chest x-ray:** Chest x-ray is not accurate in assessment of lesion size in the lung and should not be used as a method of measurement. Conventional chest CT is the preferred imaging modality to evaluate response to treatment.

- **Conventional CT and MRI:** This guideline has defined measurability of lesions on CT scan based on the assumption that CT slice thickness is 5 mm or less. If CT scans have slice thickness greater than 5 mm, the minimum size for a measurable lesion should be twice the slice thickness. MRI is also acceptable in certain situations (e.g., for body scans) however, conventional CT scan is the preferred modality to determine response to treatment.

Use of MRI remains a complex issue. MRI has excellent contrast, spatial, and temporal resolution; however, there are many image acquisition variables involved in MRI, which greatly impact image quality, lesion conspicuity, and measurement. Furthermore, the availability of MRI is variable globally. As with CT, if an MRI is performed, the technical specifications of the scanning sequences used should be optimized for the evaluation of the type and site of disease. Furthermore, as with CT, the modality used at follow-up should be the same as was used at baseline and the lesions should be measured/assessed on the same pulse sequence. It is beyond the scope of the irRECIST or RECIST 1.1 guidelines to prescribe specific MRI pulse sequence parameters for all scanners, body parts, and diseases. Ideally, the same type of scanner should be used and the image acquisition protocol should be followed as closely as possible to prior scans. Body scans should be performed with breath-hold scanning techniques, if possible.

- **Ultrasound:** Ultrasound is not useful in assessment of lesion size and should not be used as a method of measurement. Ultrasound examinations cannot be reproduced in their entirety for independent review at a later date and, because they are operator dependent, it cannot be guaranteed that the same technique and measurements will be taken from one assessment to the next. If new lesions are identified by ultrasound in the course of the study, confirmation by CT or MRI is advised. If there is concern about radiation exposure at CT, MRI may be used instead of CT in selected instances.
- **Endoscopy, Laparoscopy:** The utilization of these techniques for objective tumor evaluation is not advised. However, such techniques may be useful to confirm complete pathological response when biopsies are obtained or to determine relapse in trials where recurrence following complete response (CR) or surgical resection is an endpoint.
- **Tumor Markers:** Tumor markers alone cannot be used to assess response. If markers are initially above the upper normal limit, they must normalize for a participant to be considered in complete clinical response.
- **Cytology, Histology:** These techniques can be used to differentiate between partial responses (PR) and complete responses (CR) in rare cases (e.g., residual lesions in tumor types, such as germ cell tumors, where known residual benign tumors can remain).

The cytological confirmation of the neoplastic origin of any effusion that appears or worsens during treatment when the measurable tumor has met criteria for response or stable disease is mandatory to differentiate between response or stable disease (an effusion may be a side effect of the treatment) and progressive disease.

Appendix I Suggested Dose Modifications for Dermatologic Toxicities in Patients with Hepatocellular Carcinoma

Dermatologic Toxicity Grade	Occurrence	Suggested Dose Modification
Grade 1: Numbness, dysesthesia, paresthesia, tingling, painless swelling, erythema or discomfort of the hands or feet which does not disrupt the patient's normal activities	Any occurrence	Continue treatment with sorafenib and consider topical therapy for symptomatic relief
Grade 2: Painful erythema and swelling of the hands or feet and/or discomfort affecting the patient's normal activities	1st occurrence	Continue treatment with sorafenib and consider topical therapy for symptomatic relief If no improvement within 7 days, see below
	No improvement within 7 days or 2 nd or 3 rd occurrence	Interrupt sorafenib treatment until toxicity resolves to Grade 0–1 When resuming treatment, decrease sorafenib dose by one dose level (400 mg daily or 400 mg every other day)
	4th occurrence	Discontinue sorafenib treatment
Grade 3: Moist desquamation, ulceration, blistering or severe pain of the hands or feet, or severe discomfort that causes the patient to be unable to work or perform activities of daily living	1 st or 2 nd occurrence	Interrupt sorafenib treatment until toxicity resolves to Grade 0–1 When resuming treatment, decrease sorafenib dose by one dose level (400 mg daily or 400 mg every other day)
	3rd occurrence	Discontinue sorafenib treatment

